Another approach to obtaining a sample from the lower airways is bronchoalveolar lavage (BAL). In this procedure, a fiberoptic bronchoscope is introduced into a segmental or subsegmental bronchus until the airway is occluded proximally, and saline solution is instilled and subsequently aspirated. The fluid recovered can then be submitted for cytological and microbiological analysis. BAL is used as a diagnostic and research tool in adults with lung problems and in children and infants with underlying respiratory diseases [de Blic, 2000]. It is regarded as the best technique for microbacteriological surveillance of young children with cystic fibrosis, providing more reliable information than sampling of the upper airway with oropharyngeal/ nasopharyngeal swabs or nasal lavage [Brennan, 2008]. The main limitation of this procedure is in its invasive nature. As contamination from the upper respiratory tract flora during the procedure can sometimes occur, its capacity to describe LRTI aetiology may be challenged. Hence, a suitable cut-off should be used to avoid making spurious conclusions [Woodhead, 2005].

Recent studies reporting results from bacterial culture of BAL fluid in children with respiratory symptoms have highlighted the importance of *H. influenzae*, *S. pneumoniae*, and *Moraxella catarrhalis* in chronic or recurrent presentations of the disease (Table 1).

Table 1 Bacterial aetiology of BAL fluid culture from children with respiratory symptoms (Amended 05 October 2015)

Reference	Population	Number of samples	H. influenzae	S. pneumoniae	M. catarrhalis
[De Schutter, 2011]	Acute nonresponsive CAP (cut off $\geq 10^4$ CFU/mL)	127	26%	6.3%	8.7%
	Recurrent CAP (cut off $\geq 10^4$ CFU/mL)	123	51.2%	7.3%	21.1%
[Hare, 2010]	Bronchiectasis (cut off $> 10^4$ CFU/mL)	45	47%	18%	20%
[Marchant, 2006]	Chronic cough of > 3 weeks duration of unknown etiology	20	47%	35%	26%
[Saito, 2006]	Persistent bacterial bronchitis (persistent, wet cough for > 1 month that resolves with appropriate antibiotic treatment)	19	26.3%	21%	42.1%
[Le Bourgeois, 2002]	Severe recurrent wheezy bronchitis unresponsive to inhaled steroids	30	30%	13.33%	10%
[Marguet, 1999]	5 groups:	72 (total)			
	asthma	12	8.33%	8.33%	16.67%
	chronic cough	9	33.33%	22.22%	11.11%
	infantile wheeze	23	30.43%	0.04%	13.04%
	cystic fibrosis	10	20%	10%	-
control	10	30%	-	-	
[Schellhase, 1998]	Recurrent wheezing	27	3.7%	-	7.4%

CAP = community-acquired pneumonia

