5.6.3. Laboratory assays

Laboratory assays to characterise BAL fluid and nasopharyngeal swab samples including the detection of *S. pneumoniae*, *H. influenzae* and *M. catarrhalis* will be performed by standard techniques at GSK Biologicals' laboratory or in a validated laboratory designated by GSK Biologicals using standardised and validated procedures (refer to Table 5).

Table 5 Laboratory assays (Amended 05 October 2015)

Pathogen/ Marker	Method	Scale		Sample type	
		Qualitative	Quantitative	BAL	NP
Identification and/ or quantification of bacteria					
S. pneumoniae	Culture		X	X	X
	Molecular techniques (PCR)		X		
H. influenzae	Culture		X	X	X
	Molecular techniques (PCR) (differentiation between Hi and Haemophilus haemolyticus)†		X		
M. catarrhalis	Culture		X	X	X
	Molecular techniques (PCR)		X		
Other pathogens (if detected)	Culture	X		X	X
Serotyping of bacterial pathogens					
S. pneumoniae	Agglutination assay or molecular techniques	X		X	X
H. influenzae	Monovalent antisera	X		X	X
Antibiotic sensitivity : Including penicillin, erythromycin, azithromycin, tetracycline, levofloxacin, trimethoprim/ sulfamethoxazole, amoxicillin/ clavulanate susceptibility testing for H. influenzae, S. pneumoniae and M. catarrhalis isolated from BAL and NP swab samples; and additionally a beta-lactamase test for H. influenzae and M. catarrhalis isolated from BAL and NP swab samples; and ampicillin resistance testing by broth microdilution for beta-lactamase negative H. influenzae isolated from BAL and NP swab samples.					

†: PCR differentiation between Hi and *H. haemolyticus* will be performed on isolates from BAL/ NP swab samples that are *H. influenzae* positive

Collected samples will be used for purposes related to the quality assurance of data generated within the scope of this protocol, such as for maintenance of assays described in this protocol and comparison between analytical methods and/or laboratories.

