7.2. Sample size consideration

The proportions of *S. pneumoniae* and *H. influenzae* among all BAL fluid samples collected is expected to be between 4% and 35%, and between 7% and 51%, respectively [Schellhase, 1998; Marguet, 1999; Marchant, 2006; De Schutter, 2011].

Figure 1 provides the precision that can be expected around an estimated proportion of *S. pneumoniae* and *H. influenzae* for a sample size of at least 150 subjects. For example, the exact 95% confidence interval (CI) for an observed proportion of 11.3% is 6.7; 17.5. The exact 95% CI for an observed proportion of 33.3% is 25.9; 41.5.

Figure 1 Illustration of the lower (LL) and upper (UL) limits of the exact 95%CI built around various observed proportions for a sample of 150 subjects

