7.6.3. Analysis of secondary objectives

The distribution (with number of non-missing observations, geometric mean, standard deviation, median, minimum and maximum and number of missing observations) of the bacterial load of *H. influenzae*, *S. pneumoniae*, *M. catarrhalis* and other pathogens will be described according to the testing method (culture or PCR) and to the samples (BAL fluid sample or nasopharyngeal swab sample).

The serotype distribution (number and percentage) of *H. influenzae* **and** *S. pneumoniae* detected in BAL fluid will be presented in frequency tables.

The bacterial aetiology and serotype distribution of nasopharyngeal samples will be described along with that of BAL fluid samples.

The proportions and associated exact 2-sided 95% CI of *H. influenzae*, *S. pneumoniae*, *M. catarrhalis* and other bacterial pathogens confirmed by culture in nasopharyngeal swab will be computed for all study subjects.

For the antibiotic susceptibility, *H. influenzae*, *S. pneumoniae* **and** *M. catarrhalis* isolates (detected by culture of BAL fluid **and nasopharyngeal swab**), classified as susceptible, intermediate or resistant (following ***Clinical and Laboratory Standards Institute*** guidelines [***CLSI, 2015***]) will be tabulated by bacterial pathogen and antimicrobial agent.

(Amended 05 October 2015)

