6. STATISTICAL METHODS

All statistical analyses will be done using SAS version 9.2 or later.

Continuous variables will be described using the mean, standard deviation, median, minimum and maximum. Categorical variables will be described using frequency tables (absolute numbers and percentages for levels of each variable, excluding missing values). For continuous and categorical variables, the number of missing observations will be recorded.

All the analyses will be performed on the ATP cohort. If the percentage of subjects from the Total effective cohort with serological results excluded from the ATP cohort is more

than 5%, a second analysis of the demography and the primary objective based on the Total effective cohort will be performed to support the ATP analysis.

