6.2. Analysis of primary objective

The primary analysis will be based on the ATP cohort. If the percentage of subjects from the Total effective cohort with serological results excluded from the ATP cohort is more than 5%, a second analysis based on the Total effective cohort will be performed to support the ATP analysis.

The proportions and associated exact 2-sided 95% confidence intervals (CI) of *H. influenzae*, *S. pneumoniae*, *M. catarrhalis* and other bacteria confirmed by culture in BAL samples (*H. influenzae*, *S. pneumoniae* and *M. catarrhalis* confirmed by bacterial load >10⁴ cfu/mL if present alone or 10⁵ cfu/mL if present as co-infection) will be computed and presented for all study subjects.

The denominators will be the number of tested subjects with BAL sample results available.

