6.3. Analysis of secondary objectives

All tables related to secondary objectives 1 to 8 will be presented overall as well as by age class, gender, pneumococcal vaccination status. The age will be grouped into the following classes 6-11, 12-23, 24-35, 36-47, 48-59 and 60-71 months; however, if there are too few subjects in any of the categories, the following classification will be used of 6-23, 24-47, 48-71 months instead.

In a hospital setting and among subjects with suspected chronic LRTIs:

- 1) To describe the bacterial load of *H. influenzae*, *S. pneumoniae* and *M. catarrhalis* detected by quantitative culture and by molecular techniques (PCR) in the BAL fluid.

The distribution (with number of non-missing observations, geometric mean, standard deviation, median, minimum and maximum and number of missing observations) of the bacterial load of *H. influenzae*, *S. pneumoniae*, *M. catarrhalis* in the BAL fluid will be described according to the testing method (culture and PCR).

- 2) To describe the presence of other bacterial pathogens detected by qualitative culture in the BAL fluid.

The presence (number and percentage) of other bacterial isolates detected in BAL fluid will be presented in frequency tables.

- 3) To describe the bacterial load of *H. influenzae*, *S. pneumoniae* and *M. catarrhalis* detected by quantitative culture and by molecular techniques (PCR) in the nasopharyngeal swab samples.

The distribution (with number of non-missing observations, geometric mean, standard deviation, median, minimum and maximum and number of missing observations) of the bacterial load of *H. influenzae*, *S. pneumoniae*, *M. catarrhalis* in the nasopharyngeal swab samples will be described according to the testing method (culture and PCR).

- 4) To describe the presence of other bacterial pathogens detected by qualitative culture in the nasopharyngeal swab samples.

The presence (number and percentage) of other bacterial isolates detected in the nasopharyngeal swab samples will be presented in frequency tables.

- 5) To describe colonisation of the upper airways by characterising *H. influenzae*, *S. pneumoniae*, *M. catarrhalis* and other pathogens in nasopharyngeal swab samples.

Statistical Analysis Plan

Study alias & e-track number(s): EPI-STREP-064 BOD ES (115813)

The occurrence of *H. influenzae*, *S. pneumoniae*, *M. catarrhalis* and other pathogens detected by culture in the nasopharyngeal swab samples will be presented:

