The proportions and associated exact 2-sided 95% confidence intervals (CI) of *H. influenzae*, *S. pneumoniae*, *M. catarrhalis* and other pathogens confirmed by culture in the nasopharyngeal swab samples (*H. influenzae*, *S. pneumoniae* and *M. catarrhalis* confirmed by bacterial load $>10^4$ cfu/mL if present alone or 10^5 cfu/mL if present as co-infection) will be computed and presented for all study subjects.

The denominators will be the number of tested subjects with nasopharyngeal swab samples results available.

- 6) To determine the serotypes of *H. influenzae* and *S. pneumoniae* identified from BAL fluid and nasopharyngeal swab samples

The serotype distribution (number and percentage) of *H. influenzae* and *S. pneumoniae* isolates detected in BAL fluid will be presented in frequency tables.

The serotype distribution (number and percentage) of *H. influenzae* and *S. pneumoniae* isolates detected in nasopharyngeal samples will be presented in frequency tables.

- 7) To determine the antibiotic susceptibility profile for *H. influenzae*, *S. pneumoniae* and *M. catarrhalis* identified from BAL fluid samples.

For the antibiotic susceptibility, *H. influenzae*, *S. pneumoniae* and *M. catarrhalis* isolates (detected by culture of BAL fluid and nasopharyngeal swab) will be classified as susceptible, intermediate or resistant (following Clinical and Laboratory Standards Institute guidelines [CLSI, 2015]) see Table 2 and Table 3 below) and will be tabulated by bacterial pathogen and antimicrobial agent.

The percentage of subjects for whom antibiotic resistance test was performed and the results of the resistance test will be tabulated (Antibiotic sensitivity on BAL samples include penicillin, erythromycin, azithromycin, tetracycline, levofloxacin, trimethoprim/ sulfamethoxazole, amoxicillin/ clavulanate; and additionally a beta-lactamase test for *H. influenzae* and *M. catarrhalis*).

The ranges for antimicrobial susceptibility for *S. pneumoniae* are the following:

Table 2 MIC ranges for antimicrobial susceptibility for *S. pneumoniae*

	Susceptible (S) ($\mu\text{g/mL}$)	Intermediate (I) ($\mu\text{g/mL}$)	Resistant (R) ($\mu\text{g/mL}$)
Penicilin	≤ 0.06	0.12 – 1.00	≥ 2.0

Statistical Analysis Plan

Study alias & e-track number(s): EPI-STREP-064 BOD ES (115813)

Amoxicillin / clavulanate	$\leq 2/1$	4/2	$\geq 8/4$
Erythromycin	≤ 0.25	0.5	≥ 1
Azithromycin	≤ 0.5	1	≥ 2
Tetracycline	≤ 1	2	≥ 4
Levofloxacin	≤ 2	4	≥ 8

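### Does the lack of a rule for no-growth and below-limit results in the bacterial-load summaries call for a change to the plan?

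*SAP*

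**What the plan says.** SAP section 6.3, items 1 and 3, describes load for *H. influenzae*, *S. pneumoniae* and *M. catarrhalis*, first in BAL fluid and then in swabs, each by culture and by PCR: "The distribution (with number of non-missing observations, geometric mean, standard deviation, median, minimum and maximum and number of missing observations) of the bacterial load". Protocol section 7.6.3 has the same list: "The distribution (with number of non-missing observations, geometric mean, standard deviation, median, minimum and maximum and number of missing observations". The general rule in SAP section 6 adds only that "For continuous and categorical variables, the number of missing observations will be recorded". I found no rule for no-growth or below-limit loads in SAP sections 6, 6.3, 7.1 or 7.2, or in Protocol sections 7.4 and 7.6. No assay limit is given, and the scale of the standard deviation is not stated.

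Presence of the organisms is analysed separately. For BAL, SAP section 6.2 plans proportions with exact 95% intervals, and "The denominators will be the number of tested subjects with BAL sample results available". SAP section 6.3, item 5, does the same for swabs. For the three main organisms, both count a sample only when it is "confirmed by bacterial load $>10^4$ cfu/mL if present alone or 10^5 cfu/mL if present as co-infection". No proportion is planned for PCR.

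**The concern.** A geometric mean is undefined, or zero, as soon as one observation is zero. Most BAL samples are expected to be negative for a given organism: Protocol section 7.2 says the proportion with *S. pneumoniae* and *H. influenzae* "is expected to be between 4% and 35%, and between 7% and 51%, respectively". So the question arises in nearly every load table, and three readings are open on paper:

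- Negatives enter as zero. The geometric mean fails, or software drops them and it rests on fewer samples than the count and median beside it.
- Negatives are coded missing. The missing count then mixes tested-negative samples with untested ones.
- Negatives get a substituted value. The result then depends on that value and on how common the organism is, so two age groups with equal load among positives would differ merely because detection differs.

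At stake are secondary objectives 1 and 3, whose tables are repeated by age class, gender and pneumococcal vaccination status.

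**Working it through.** **1. The plan's own figures.** No load figure is stated. The nearest computed figures are the exact intervals in Protocol section 7.2. Clopper-Pearson limits give 6.74% to 17.52% for 17/150 = 11.3%, and 25.86% to 41.48% for 50/150 = 33.3%. Both match the stated 6.7; 17.5 and 25.9; 41.5.

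**2. Will there be non-detects?** At the top expected rate, 51%, the chance that all 150 samples are positive is 0.51^150 = 1.4 × 10^-44. Some source rates in Protocol Table 1 use a cut-off, for example "Recurrent CAP (cut off $\geq 10^4$ CFU/mL", so true detection may be higher. At an assumed 95% detectable, the chance of at least one non-detect is 1 − 0.95^150 = 0.9995; at an assumed 98%, 1 − 0.98^150 = 0.952. Non-detects should be expected.

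**3. How much would the rule matter?** Let p be the share detected, L the geometric mean among detected samples and c the value given to the rest. Then log10(GM) = p·log10(L) + (1 − p)·log10(c). L = 10^5 per mL and the values of c are assumptions; the documents give neither.

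| Share detected | negatives left out | c = 100 | c = 10 | c = 1 |
|---|---|---|---|---|
| 33.3% | 100,000 | 1,000 | 215 | 46 |
| 11.3% | 100,000 | 219 | 28 | 3.7 |

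For example, at one third detected and c = 100: 5/3 + (2/3) × 2 = 3, so GM = 1,000. More generally, multiplying c by ten multiplies the geometric mean by 10^q, where q = 1 − p: 3.2 at q = 50% and 6.3 at q = 80%. The standard deviation moves too. With an assumed log10 SD of 1 among positives and p = 1/3, the overall variance is p + p(1 − p)(5 − log10 c)². The SD is then √(0.333 + 2.000) = 1.53 at c = 100 and √(0.333 + 5.556) = 2.43 at c = 1. If negatives are kept and fewer than half the samples are positive, the median is simply c.

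**4. Which reading would be used?** The wide range in step 3 comes from substitution, and neither document mentions substituting a value. Entering zeros fails visibly. What remains is to summarise the samples in which the organism was found. This also fits the objective printed above each load sentence in SAP section 6.3, which speaks of load detected by culture and by PCR. On that reading the geometric mean is L whatever the detection rate, and strata with equal load among positives agree.

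**5. Can negatives and untested samples be told apart?** For culture, yes: the number of samples taken is tabulated (SAP section 6.1.7), the number tested is the denominator in SAP sections 6.2 and 6.3, item 5, and the load table's non-missing count is the number with a load. For PCR, the non-missing count by method gives the number with a load, but the number tested has to be inferred from the samples taken.

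**6. Sparse strata.** With six equal age classes (150/6 = 25) and 4% positive, the chance of at most one positive is 0.96^25 + 25 × 0.04 × 0.96^24 = 0.74. The SAP falls back to three classes when numbers are too few (150/3 = 50), and the same sum is then 0.96^50 + 50 × 0.04 × 0.96^49 = 0.40. Equal class sizes are assumed.

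**The case for a change.** The strongest case for a change is that the analysis sentence speaks of missing and non-missing observations without limiting them to positives, while tested negatives are treated as results elsewhere: they stay in the denominators of SAP section 6.2 and form the culture-negative subgroups of SAP section 2. The rule can move the answer by three or four powers of ten, settling it now avoids a choice made after seeing the data, and it costs only wording.

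Part of this stands. The rule is absent, the objective's wording suggests positives only without settling it, the SAP plans no any-growth culture proportion for the three main organisms, and there is no PCR detection proportion. The rest is weaker. The denominators and subgroups concern positive or negative status; they do not show that a negative sample carries a load value. It is too broad to say that no detection rate is planned, given the culture proportions in SAP sections 6.2 and 6.3, item 5, and Protocol section 7.6.3 plans the swab proportion without restating a cut-off. Nor does the footnote to Protocol Table 5 limit who is tested by PCR: the step that "will be performed on isolates from BAL/ NP swab samples that are *H. influenzae* positive" is the separation of *H. influenzae* from *H. haemolyticus* on isolates, not the quantification of load.

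**Conclusion.** This is missing detail that an analyst fills sensibly, not an error. No stated rule yields a wrong number. The zero problem announces itself the first time the table is run, and the natural answer, load among detected samples, is the one the objectives point to. The spread of 46 to 100,000 per mL at one third detected is the size of the ambiguity on paper, under an assumed geometric mean of 10^5 per mL among positives and negatives set as low as 1. It is not the expected error, because most of it requires a substitution that nobody has proposed. The other possible additions (a PCR count and percentage, a log-scale standard deviation, listing values in sparse strata) are extras or presentation choices usually settled in table shells. They would change no conclusion in a descriptive secondary table that carries no test or interval on load. The primary proportions and the sample size are unaffected.

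Two limits apply. The documents give no detection rate for PCR or for swabs, so the size there is unknown. The table templates annexed to the SAP are not in the public set and may already hold the rule.

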1. INTRODUCTION

1.1. Background

Lower respiratory tract infections (LRTIs) such as pneumonia and bronchitis, are important causes of childhood morbidity and mortality worldwide [Mulholland, 2007; Obaro, 2006; Rudan, 2004]. Determining the aetiology of LRTIs in children has always been a challenge due to the difficulty in obtaining a sample from the lungs. *Streptococcus pneumoniae* and *Haemophilus influenzae* are considered to be the main bacterial pathogens associated with lobar pneumonia, and their importance in disease was described in studies using transthoracic needle aspiration (lung tap), in which a sample was collected directly from the site of infection, *i.e.* the section of consolidation. Studies using this technique to describe non-consolidated infections such as broncho-pneumonia are less frequent. Lung taps are now rarely used because the potential risk to patients is considered unnecessary and LRTIs can be treated with empiric antibiotics [Hausdorff, 2008]. Thus, there have been attempts to use other less-invasive techniques for describing bacterial aetiology.

Among the non-invasive procedures, blood culture is the most widely used. It is routinely performed in patients hospitalised with moderate or severe pneumonia, but this procedure yields evidence of a pathogen in only 10-15% of the cases [Mccracken, 2000]. Moreover, since blood culture may not be performed for non-hospitalised cases, the role of un-encapsulated (non-typeable) *H. influenzae* strains in causing LRTIs may be underestimated [Shann, 1999].

Sputum samples, which are considered the best non-invasive alternative for detecting bacterial causes of LRTIs in adults, can rarely be collected in children because they often have difficulties producing sputum. Thus, the simplest approach of describing the aetiology of LRTI has been through the collection of nasopharyngeal samples in symptomatic children. Nevertheless, because the main bacteria associated with infection are also common colonisers of the nasopharynx, the specificity of such samples alone as a measurement of aetiology is considered low.

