7. DATA EVALUATION: CRITERIA FOR EVALUATION OF OBJECTIVES

7.1. Endpoints

7.1.1. Primary endpoint

- Occurrence of *H. influenzae*, *S. pneumoniae*, *M. catarrhalis* and other bacteria in BAL fluid samples of subjects aged ≥ 6 months to < 6 years with suspected chronic LRTIs and an indication for BAL
 - *H. influenzae*, *S. pneumoniae* and *M. catarrhalis* confirmed by bacterial load $>10^4$ cfu/mL if present alone or 10^5 cfu/mL if present as co-infection.

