4.2. Secondary endpoints

In a hospital setting and among subjects aged ≥ 6 months to < 6 years with suspected chronic LRTIs and an indication for BAL:

- 1) Bacterial load of *H. influenzae*, *S. pneumoniae* and *M. catarrhalis* in the BAL fluid as determined by quantitative culture and PCR.
- 2) Description of other bacterial pathogens in the BAL fluid as determined by qualitative culture.
- 3) Bacterial load of *H. influenzae*, *S. pneumoniae* and *M. catarrhalis* in nasopharyngeal swab samples as determined by quantitative culture and PCR.
- 4) Description of other bacterial pathogens in nasopharyngeal swab samples as determined by qualitative culture.
- 5) Occurrence of *H. influenzae*, *S. pneumoniae*, *M. catarrhalis* and other pathogens detected by culture in the nasopharyngeal swab samples.
- 6) Occurrence of *H. influenzae* and *S. pneumoniae* serotypes identified from BAL fluid samples and nasopharyngeal swab samples.
- 7) Occurrence of *H. influenzae*, *S. pneumoniae* and *M. catarrhalis* minimum inhibitory concentration (MIC) values identified from BAL fluid and nasopharyngeal swab samples.
- 8) Demographic characteristics (age, gender, etc), clinical characteristics (including medical history, LRTI symptoms, treatment history, vaccination status, etc),

radiological evidence and laboratory results (including white blood cell counts, CRP level and erythrocyte sedimentation rate, if available).

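### SAP 6.3 item 5 applies the BAL load cut-offs to nasopharyngeal swabs, so upper-airway colonisation can only be understated

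*SAP*

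**What the plan says.** The NP occurrence endpoint appears in Protocol 7.1.2 and SAP 4.2 item 5. Both cover the three named species and "other pathogens detected by culture in the nasopharyngeal swab samples". Neither sets a load threshold. The protocol's own analysis sentence (7.6.3) asks for proportions with exact 95% CIs by culture of the swab, again with no threshold.

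SAP 6.3 item 5 opens in the same terms ("detected by culture in the nasopharyngeal swab samples will be presented"). Its next sentence then computes the proportions as "confirmed by culture in the nasopharyngeal swab samples (*H. influenzae*, *S. pneumoniae* and *M. catarrhalis* confirmed by bacterial load $>10^4$ cfu/mL" if alone, or 10^5 cfu/mL in co-infection. On the denominator it says: "The denominators will be the number of tested subjects with nasopharyngeal swab samples results available".

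The load rule otherwise appears only for BAL: under the primary endpoint in Protocol 7.1.1 ("cfu/mL if present as co-infection") and SAP 4.1, and in SAP 6.2 for organisms "confirmed by culture in BAL samples". SAP Section 9 lists no change from the planned analyses.

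**The concern.** A load cut-off separates infection from contamination in a lower-airway sample. Protocol 1.1 gives that reason and no other: "As contamination from the upper respiratory tract flora during the procedure can sometimes occur", so a suitable cut-off is needed for BAL. Objective 5 asks a different question, namely which organisms colonise the upper airway. The protocol says of these species that "the main bacteria associated with infection are also common colonisers of the nasopharynx". Requiring a high load removes some of the carriage that the objective sets out to describe.

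The objective 5 proportions are at stake, overall and repeated by age class, gender and pneumococcal vaccination status. The report could also look inconsistent. The NP load, serotype and susceptibility tables in SAP 6.3 carry no threshold, so a child could supply an NP serotype and still not count as positive in the objective 5 table.

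**Working it through.** **1. Definitions side by side**

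| Place | Sample | Load rule |
|---|---|---|
| Protocol 7.1.1, SAP 4.1, SAP 6.2 | BAL | yes |
| Protocol 7.1.2, SAP 4.2 item 5 | NP | none |
| Protocol 7.6.3 (NP proportions) | NP | none |
| SAP 6.3 item 5, lead-in | NP | none |
| SAP 6.3 item 5, computation | NP | **yes** |
| SAP 6.3 items 3, 6 and 7 (load, serotype, susceptibility) | NP | none |

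Only one NP line carries the rule, and its parenthesis matches the one in SAP 6.2 for BAL.

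**2. The plan's own precision figures**

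The exact (Clopper-Pearson) limits for x of n are: lower = 2.5% quantile of Beta(x, n − x + 1); upper = 97.5% quantile of Beta(x + 1, n − x). With n = 150 (Protocol 7.2):
- 17/150 = 11.3%, CI 6.7 to 17.5
- 50/150 = 33.3%, CI 25.9 to 41.5

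Both agree with Protocol 7.2. The documents give no figure for NP carriage.

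**3. Direction**

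Swabs above the cut are a subset of culture-positive swabs, and the denominator does not change. Let p be the proportion detected by culture and s the share of those below their applicable cut. The reported proportion is then p × (1 − s) ≤ p, with equality only if s = 0.

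**4. Size (p and s are assumed; the documents give neither)**

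Take n = 150 and p = 40%, so 60 children are colonised:

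| s | Counted | Reported | Exact 95% CI |
|---|---|---|---|
| 0 | 60 | 40.0% | 32.1 to 48.3 |
| 10% | 54 | 36.0% | 28.3 to 44.2 |
| 25% | 45 | 30.0% | 22.8 to 38.0 |
| 50% | 30 | 20.0% | 13.9 to 27.3 |

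At s = 25% and other values of p, with counts rounded to whole children:
- p = 30%: 34/150 = 22.7%
- p = 50%: 56/150 = 37.3%
- p = 70%: 79/150 = 52.7%

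For scale, the CI half-width at 60/150 is (48.3 − 32.1)/2 = 8.1 points, and s = 25% shifts the estimate by 10.0 points. This compares bias with precision. It is not a test, since the counts are nested in the same children.

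**5. Co-colonised children**

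Their cut is ten times higher. Suppose log10 load is normal with SD 1 and has the same distribution in sole and co-carriers (assumed). The shares passing >10^4 and 10^5 are then 50% and 16% at mean 4, 84% and 50% at mean 5, and 98% and 84% at mean 6. One species' reported carriage would then depend on whether another species is present.

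**6. Mixed definitions in one table**

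Protocol Table 5 plans only qualitative culture for other pathogens, so no load rule can apply to them. The objective 5 table would show thresholded proportions for three species beside unthresholded ones for the rest.

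**The case against.** The strongest counter-argument is textual. Protocol 7.6.3 says *confirmed* by culture for NP swabs, and the protocol uses that verb with the load rule for BAL. The BAL analysis in Protocol 7.6.2 does not repeat the threshold either, yet the rule governs it. On this reading the SAP only spells out what *confirmed* means. It does not hold: the BAL analysis inherits the rule from its own endpoint, whereas the NP endpoint says *detected* and has no rule to inherit.

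A second argument is purpose. Protocol 1.2 hopes to link NP findings to BAL culture, and a common rule would give a like-for-like comparison. That would be a fair reason for an additional thresholded row, but neither document states it, and objective 5 is about colonisation.

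Three limits stand. The bias is zero if no positive swab falls below its cut. The extra loss in co-colonised children depends on their loads, which may differ from those of sole carriers. The unthresholded load, serotype and susceptibility tables keep low-load isolates visible, but they do not give the carriage proportion with an exact CI that Protocol 7.6.3 promises.

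**Conclusion.** The concern holds. As written, SAP 6.3 item 5 does not estimate the endpoint it is meant to serve. For the three named species the result cannot exceed the proportion detected by culture, and it is lower as soon as one positive swab misses its cut. The amount cannot be derived from the documents; the figures above rest on assumed carriage and assumed losses. The demonstrated effect is confined to the objective 5 occurrence tables and their subgroup repeats, which are descriptive. The primary BAL analysis and the sample size are not affected. It should be corrected before analysis.

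**What to change.** In SAP 6.3 item 5, delete the parenthesis with the load rule. Define NP occurrence as detection by culture at any load, with exact 95% CIs over children who have an NP culture result, and keep the load rule for BAL. If a thresholded NP proportion is wanted, for example for comparison with BAL, add it as a separately labelled row, state the reason, and list it in SAP Section 9.

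In the same edit, confirm which definition and which sample set the NP positive and negative strata in SAP 6.3 item 8. SAP Section 2 defines species status by culture positivity without naming the sample.

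The cost is SAP wording and the matching table shell. Quantitative NP culture is already planned, so no new data or assays are needed.
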